2.1.1.6 Age  $\geq 18$  years

2.1.1.7 ECOG performance status  $\leq 2$  (see [Appendix A](#)). **NOTE:** In participants with neurologic deficits caused by CNS lymphoma any ECOG status is acceptable to be eligible.

2.1.1.8 Participants must have adequate organ and marrow function as defined below:

absolute neutrophil count	$\geq 1000 \text{ cells}/\text{mcL} (1 \times 10^9/\text{L})$
platelet count	$\geq 50,000 \text{ cells}/\text{mcL} (50 \times 10^9/\text{L})$
hemoglobin	$> 8.0 \text{ g/dL}$ (transfusions permitted)
total bilirubin	$\leq 1.5 \times$ upper limit of normal (ULN) (unless Gilbert's syndrome or disease infiltration of the liver is present)
Aspartate Aminotransferase or serum glutamic-oxaloacetic transaminase/ Alanine Aminotransferase or serum glutamic pyruvic transaminase AST(SGOT)/ALT(SGPT)	$\leq 3.0 \times$ institutional ULN for those without lymphoma involvement OR $\leq 5.0 \times$ institutional ULN for those with lymphoma involvement
Serum Creatinine OR creatinine clearance (Cr Cl)	$\leq 1.5 \text{ mg/dL}$ OR $\geq 40 \text{ ml/min}/1.73\text{m}^2$

NOTE: Cr Cl will be calculated with the use of the 24-hour creatinine clearance or eGRF in the clinical lab

Laboratory assessments to determine eligibility may be performed at CLIA (or equivalent) certified laboratories outside the NIH and results forwarded to the study team for review and management. Given that the methodologies utilized are similar across all laboratories, no significant variability is expected and there is no anticipation that study data will be affected. However, as different laboratories use slightly different kinds of equipment, each laboratory must determine/validate its own reference ranges. Therefore, on this protocol, normal ranges from each lab will be used in reference to terms such as ULN, except in cases where absolute values are appropriate and are specified as such

2.1.1.9 Prothrombin time (PT) and activated partial thromboplastin time (aPTT) must be < 1.5 x the ULN; except if, the aPTT is prolonged because of a positive Lupus Anticoagulant.

2.1.1.10 Participants must agree to use certain methods of birth control. A “highly effective method of birth control” for participants of childbearing potential is defined as a method that has a low failure rate (i.e., less than 1% per year) when used consistently and correctly and includes implants, injectables, birth control pills with two hormones, some intrauterine devices (IUDs). Participant who can father children are required to use barrier. The specific guidelines are as follows:

- Individuals of childbearing potential (IOCBP), defined as a sexually mature individual who: 1) has not undergone a hysterectomy or bilateral oophorectomy; or 2) has not been naturally postmenopausal (amenorrhea following cancer therapy does not rule out childbearing potential) for at least 24 consecutive months (i.e., has had menses at any time in the preceding 24 consecutive months), must either commit to continued abstinence from heterosexual intercourse or begin TWO acceptable methods of birth control, one highly effective method and one additional effective method AT THE SAME TIME, at least 28 days before starting Revlimid®, as well as for the duration after the last dose of study drug as listed below. For more details see **Appendix C**.
- Individuals who can father children must agree to remain abstinent (refrain from heterosexual intercourse) or use contraceptive measures as outlined in **Appendix C** to prevent pregnancy of their partner and should also agree to not donate sperm while taking the study treatment and for the durations as listed below.

Contraception Requirements		
Time frame/Study Drug	Individuals of childbearing potential	Individuals who can father children
Pre-Treatment/During Treatment	Time frame prior to/during dosing:	
All drugs	Begins 28 days prior to treatment	Begins on day 1
Post-Treatment	Time frame after the last dose:	
Venetoclax	90 days	90 days
Ibrutinib	3 months	3 months
Obinutuzumab	18 months	6 months
Revlimid®	28 days	28 days

2.1.1.11 All study participants must be registered into the mandatory Revlimid REMS™ program and be willing and able to comply with the requirements of Revlimid REMS™.

2.1.1.12 Nursing participants must be willing to discontinue nursing from study treatment initiation through designated time points after study drugs discontinuation (as required in the table above)

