## 2 ELIGIBILITY ASSESSMENT AND ENROLLMENT

### 2.1 ELIGIBILITY CRITERIA

#### 2.1.1 Inclusion Criteria

2.1.1.1 Participants must have histologically or cytologically confirmed primary diffuse large B-cell lymphoma of the CNS (PCNSL) or non-GCB diffuse large B-cell lymphoma with secondary involvement of the CNS (SCNSL). **NOTE:** Participants with B-cell lymphomas that were previously indolent but now involve the CNS (i.e., transformed

from previous follicular lymphoma, chronic lymphocytic leukemia, marginal zone lymphoma, and mantle cell lymphoma) **are eligible**.

2.1.1.2 Participants must have a disease that is relapsed or refractory after initial systemic treatment or be considered ineligible for standard frontline therapy with high-dose methotrexate due to one of the following criteria:

- Age  $\geq$  70 years
- Estimated glomerular filtration rate  $< 60 \text{ ml/min}/1.73\text{m}^2$
- Presence of ascites or pleural effusion

2.1.1.3 Participants must have evaluable disease by clinical exam (i.e., palpable lymphadenopathy, measurable skin lesions, etc.) and/or imaging (measurable lymph nodes or masses on CT or MRI and/or evaluable FDG-avid lesions on PET).

2.1.1.4 Participants with second malignancies not requiring active systemic therapy or premalignant conditions such as monoclonal B-cell lymphocytosis (MBL) or monoclonal gammopathy of undetermined significance (MGUS) are eligible.

2.1.1.5 Participants that are positive for hepatitis B core antibody (HBcAb), hepatitis B surface antigen (HBsAg), or hepatitis C antibody must have a negative hepatitis B and/or C viral load by polymerase chain reaction (PCR). See Section [4.1.2](#).

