#### 2.3.2.2 Arms

Number	Name	Description
1	Experimental- lenalidomide + nivolumab window; followed by VIPOR-Nivo (Closed on 06/06/2022)	Nivolumab on day 1 with lenalidomide (days 1-14) for a 21-day cycle. Following Window, VIPOR-Nivo (venetoclax, ibrutinib, prednisone, obinutuzumab, lenalidomide, and nivolumab) in 21-day cycles for up to 6 cycles
2	Experimental- VIPOR	VIPOR (venetoclax, ibrutinib, prednisone, obinutuzumab, and lenalidomide) in 21-day cycles for up to 6 cycles

**\*NOTE:** participants with CrCl >60 mL/min will receive lenalidomide 15mg (dose level 1) while those with CrCl >40 mL/min and <60mL/min will receive lenalidomide 10mg (dose level -1) (Table 3).

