### 3.1.1 Study Schema

## 3.2 DRUG ADMINISTRATION

After enrollment participants will proceed to induction therapy. A maximum of 6 cycles of induction therapy will be given every 21 days with the following dosing schedule:

- Obinutuzumab 1000 mg IV rate escalated infusiona on days 1 and 2
- Prednisone 100 mg PO daily days 1-7 (approximately 30-60 minutes prior to obinutuzumab infusion on days 1 and 2)
- Ibrutinib 560 mg PO daily days 1-14
- Lenalidomide 15 mg PO daily days 1-14 (if CrCl > 60 mL/min) or 10 mg PO daily days 1-14 (if CrCl < 60 mL/min but > 40 mL/min)
- Venetoclax 800 mg PO daily on days 1-14
- Acetaminophen 650 mg PO daily on days 1 and 2 (approximately 30-60 minutes prior to Obinutuzumab infusion)
- Diphenhydramine 50 mg PO daily on days 1 and 2 (approximately 30-60 minutes prior to Obinutuzumab infusion)
- Peg-filgrastim 6 mg subcutaneous once on day 8 only

a Obinutuzumab infusion starting at 50 mg/hr with rate increase by 50 mg/hr every 30 minutes as tolerated to a maximum rate of 400 mg/hr. If tolerated, subsequent infusions may start at 100 mg/hr with rate increase by 100 mg/hr every 30 minutes to a maximum rate of 400 mg/hr. Monitor participants closely for signs/symptoms of the infusion reaction and interrupt/discontinue infusion for any signs of a reaction and contact the investigator.

For more details see Section [14](#)

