#### 3.3.1 Criteria for Starting a New Cycle of Study Therapy

A new course of study treatment may begin on Day 1 of a new cycle if:

- ANC  $\geq$  1000/ $\mu$ L and
- Platelet count  $\geq$  50,000/ $\mu$ L and
- CrCl  $>$  40 mL/min
- No drug-related  $\geq$  Grade 3 toxicity

If the criteria are not met, assessments may be repeated after 1 week. The initiation of a new cycle of study therapy should be delayed until participant meets criteria to receive study drug as planned.

A dose delay of up to 6 weeks from the planned start of an induction cycle is permitted to allow recovery of toxicities. Actions for recurrent hematologic adverse events are described in the tables for each drug in the sections below (lymphopenia is not considered a hematologic toxicity, as it is an expected outcome of therapy). If treatment is delayed for more than 6 weeks, the participant should be withdrawn from the study treatment.

If one of the study drugs is discontinued because of toxicity as addressed below, participant will continue treatment with other drugs. If two or more drugs are discontinued, participants will be taken off study treatment.

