Hyperthyroidism or hypothyroidism $\geq$ Grade 2	

Hold lenalidomide.

Evaluate etiology & initiate appropriate therapy.

Reduce lenalidomide by 1 dose level at Day 1 next cycle. Start new cycle when participant meets cycle initiation criteria.

Event(s)	Dose Delay or Modification during a cycle
Creatinine Clearance <60 mL/min (CrCl, Cockcroft-Gault)	

-CrCl 30–60 mL/min: 10 mg every 24 hours

-CrCl <30 mL/min: hold lenalidomide

• If CrCl becomes >60mL/min for a minimum of 2 cycles, may escalate to the prior dose at investigator's discretion.

Any other Grade 4 toxicity or unmanageable Grade 3 toxicity attributed to lenalidomide	

• Hold lenalidomide.

-If improves to <math>\leq</math> Grade 2 in <math>\leq</math> 7 days, administer full dose of study treatment for the next cycle.

-If improves to <math>\leq</math> Grade 2 in <math>></math> 7 days, reduce the dose of lenalidomide by 1 dose level.

• For subsequent episodes, dose reduction 2 of lenalidomide and drug discontinuation will be considered.

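### Entry on creatinine at or below 1.5 mg/dL alone can admit a participant with CrCl of 40 mL/min or less, who has no stated lenalidomide starting dose and cannot begin any cycle governed by section 3.3.1

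*Combined protocol and SAP*

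**What the plan says.** All references are to the combined protocol and SAP.

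- **Entry (2.1.1.8).** The row "Serum Creatinine OR creatinine clearance (Cr Cl" is met by creatinine at or below 1.5 mg/dL, or by CrCl of at least 40 ml/min/1.73m2. A note on method reads "Cr Cl will be calculated with the use of the 24-hour creatinine clearance or eGRF in the clinical lab". Section 2.2.2.2 calls for a 24-hour collection only where creatinine exceeds 1.5 mg/dL. No exclusion criterion in 2.1.2 sets a CrCl floor.
- **Who is recruited (2.1.1.2).** Besides relapsed or refractory disease, a participant may enter as unfit for high-dose methotrexate. The qualifying reasons include age 70 or over, and "Estimated glomerular filtration rate" below 60.
- **Starting dose (2.3.2.2 and 3.2).** Lenalidomide is 15 mg for CrCl above 60. The arm note adds that "those with CrCl >40 mL/min and <60mL/min will receive lenalidomide 10mg (dose level -1", and 3.2 agrees: "10 mg PO daily days 1-14 (if CrCl < 60 mL/min but > 40 mL/min". No other band appears.
- **Cycle start (3.3.1).** "A new course of study treatment may begin on Day 1 of a new cycle if" introduces a list that includes CrCl above 40 mL/min, with no creatinine alternative. Assessments may be repeated after a week. "If treatment is delayed for more than 6 weeks, the participant should be withdrawn from the study treatment"; section 3.8.1 allows the Principal Investigator an exception in exceptional circumstances.
- **In-cycle changes (Table 5).** Under the column "Dose Delay or Modification during a cycle", CrCl by Cockcroft-Gault of 30 to 60 gives 10 mg, and below 30 the drug is held.

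**The concern.** The entry rule and the treatment rules use different renal tests. Creatinine alone opens the door, but CrCl alone sets the dose and permits a cycle. In older or lighter people, a creatinine within the limit can go with a CrCl at or below 40. The plan can then enrol someone for whom it states no lenalidomide starting dose and whose next cycle it forbids.

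The immediate stake is safe, consistent prescribing: the plan adjusts lenalidomide for renal function, and staff would have to improvise a dose for an eligible participant. The secondary stake is a wasted enrolment. Section 10.2.1 allows for only 2 inevaluable participants beyond the 10 needed, and someone who enters but cannot start uses one of those places.

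**Working it through.** **1. The plan's own figure.** The rule in 10.2 is 7 or more successes among 10.

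- At a true rate of 50%: (120 + 45 + 10 + 1)/1024 = 176/1024 = 0.172.
- At 80%: 120 × 0.8^7 × 0.2^3 + 45 × 0.8^8 × 0.2^2 + 10 × 0.8^9 × 0.2 + 0.8^10 = 0.201 + 0.302 + 0.268 + 0.107 = 0.879 (before rounding of the terms).

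Both match the stated 17.2% and 87.9%. Nothing below changes them.

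**2. The renal rules side by side.** Units are treated as interchangeable here.

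| CrCl | Eligible if creatinine ≤1.5 | Eligible if creatinine >1.5 | Starting dose (2.3.2.2, 3.2) | New cycle (3.3.1) |
|---|---|---|---|---|
| above 60 | yes | yes | 15 mg | allowed |
| exactly 60 | yes | yes | none stated | allowed |
| above 40, below 60 | yes | yes | 10 mg | allowed |
| exactly 40 | yes | yes | none stated | not allowed |
| below 40 | yes | no | none stated | not allowed |

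The last two rows are the conflict. The exactly-60 row is a smaller gap of the same kind.

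**3. Can creatinine at or below 1.5 go with CrCl at or below 40?** Cockcroft-Gault, the only formula the protocol names (Table 5), is (140 − age) × weight in kg / (72 × creatinine), times 0.85 for women. Ages, weights and creatinine values are assumptions.

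- Man, 70 y, 60 kg, creatinine 1.5: 70 × 60/(72 × 1.5) = 4200/108 = 38.9 mL/min.
- Woman, 75 y, 60 kg, creatinine 1.2: 65 × 60 × 0.85/(72 × 1.2) = 3315/86.4 = 38.4.
- Woman, 80 y, 50 kg, creatinine 1.0: 60 × 50 × 0.85/72 = 35.4.
- Range at creatinine 1.5, ages 70 to 80, 50 to 80 kg: 23.6 to 44.1 in women, 27.8 to 51.9 in men.
- At creatinine 1.0 and age 75, a woman of 65 kg gives 65 × 65 × 0.85/72 = 49.9 and a man of 70 kg gives 65 × 70/72 = 63.2. Both are inside a dosing band.

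So some eligible people fall at or below 40 and others do not. Cockcroft-Gault is not the entry method. The protocol names no eGFR equation, and a laboratory eGFR may place a given person differently.

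**4. Does 3.3.1 cover cycle 1?** The text does not say. Laboratory tests within 24 hours before Cycle 1 Day 1 (3.4.1) fit a reading that it does. The 3.3.1 item on drug-related toxicity fits a reading that it begins at cycle 2. On the first reading, a participant with CrCl at or below 40 cannot start while it stays there. On the second, cycle 1 has no stated starting dose, and cycle 2 is barred while CrCl stays there.

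**The case against.** The strongest reply is that the problem would be noticed. eGFR is on the acute care panel at screening and on Day 1 of each cycle, 2.1.1.8 accepts it as CrCl, and lenalidomide dosing depends on CrCl for everyone. A value of 40 or less should prompt a query before the first dose, at a single site whose team discusses participants about weekly. That stands, and it lowers the severity. It does not remove the conflict: seeing a low value does not make the participant ineligible under an either-or criterion.

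A second reply is that Table 5 already gives 10 mg for CrCl 30 to 60. It shows that the authors accept that dose in that range, but only as a change during a cycle. It sets no starting dose and does not lift the bar in 3.3.1. Extending the 10 mg starting band downward and relaxing 3.3.1 would also remove the conflict without narrowing entry. That is a clinical choice.

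Two stronger readings are tempting. A reader might infer that the primary endpoint loses power. That would need 3.3.1 to exclude cycle 1, the team to dose someone despite having no stated dose, CrCl to stay at or below 40 beyond the 6-week delay, no 3.8.1 exception, and the withdrawal to be scored as a non-success. The last step is unclear, because the 10.4.2 definition turns on stopping for toxicity, and low CrCl at entry is not drug toxicity. The documents give no frequency for any of these steps. A reader might also infer that, because entry uses values per 1.73 m2 and later rules use mL/min, smaller people with entry values somewhat above 40 are caught too. The protocol prescribes no such conversion. The unit mismatch is worth tidying, but it establishes no affected group.

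**Conclusion.** Wrong as written, at low to moderate severity. Followed literally, the plan can enrol a participant with CrCl at or below 40 for whom it states no lenalidomide starting dose, and who cannot begin any cycle governed by 3.3.1 while CrCl stays there. This is a conflict between stated rules, and it follows from the text without any assumption about patients.

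That such participants are plausible rests on the age and eGFR entry routes and on the assumed examples. How many there would be is unknown, and many older participants with lower creatinine would sit comfortably inside a dosing band. The case for change is prescribing clarity and avoiding unusable enrolments. The sample size, the 7-of-10 rule and its operating characteristics stand.

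**What to change.** 1. In 2.1.1.8, require CrCl above 40 mL/min of every participant, whatever the creatinine. Keep the existing measurement options: laboratory eGFR, or a 24-hour collection when needed.
2. Use the same measure and unit for entry, starting dose and cycle start. A mandatory switch to Cockcroft-Gault is not needed.
3. In 2.3.2.2 and 3.2, define the 10 mg band as above 40 and up to and including 60.
4. State in 3.3.1 that the renal criterion applies to cycle 1.

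The clinical team should confirm the limit of 40. Table 5 can stay as the rule for changes during a cycle.

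The cost is an amendment with IRB approval, as the Statement of Compliance requires. No new test is needed, since eGFR is already reported at screening and on each Day 1. The downside is slightly narrower eligibility: people with creatinine at or below 1.5 mg/dL but CrCl of 40 or less, and those at exactly 40, would no longer enter.

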## 2.1.2 Exclusion Criteria

2.1.2.1 Participants with plasmablastic lymphoma and B-cell lymphoma, unclassifiable, with features intermediate between DLBCL and classical Hodgkin lymphoma are not eligible.

2.1.2.2 Chemotherapy (excluding corticosteroids), radiation therapy, and/or monoclonal antibody ≤ 7 days prior to first administration of study treatment. Rationale for a short 7-day window is that participants with relapsed CNS lymphomas often have existing neurologic conditions that mandate urgent therapy.

2.1.2.3 Previous treatment with more than one of the following classes of medications: (1) BTK inhibitors, (2) BCL2 inhibitors, (3) immunomodulatory imide drugs (IMIDs) (including lenalidomide and pomalidomide).

2.1.2.4 Participants who require continuous treatment with a strong CYP3A inhibitor/inducer (i.e., with the exception of any medication to be specifically studied in this protocol).

- **NOTE:** A comprehensive list of inhibitors, inducers, and substrates may be found at: <https://drug-interactions.medicine.iu.edu/MainTable.aspx>

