### 2.2.2 Screening activities performed after a consent for screening has been signed

The following activities will be performed only after the participant has signed this study consent. Assessments performed at outside facilities or on another NIH protocol within the timeframes below may also be used to determine eligibility once a participant has signed the consent.

Assessments and procedures to confirm study eligibility should be completed within 28 days prior to treatment initiation (unless otherwise noted).

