## 6.3 RESPONSE CRITERIA

Although response is not the primary endpoint of this trial, participants with measurable disease will be assessed by standard criteria. For the purposes of this study, participants should be re-evaluated as outlined in [Appendix D: Study Calendar](#)

. In addition to a baseline scan, restaging scans will be performed after cycles 1, 3, and 6. Cases with complete resection of tumor mass will not be evaluable for response assessment; however, will be included in the PFS and OS statistics. When appropriate, for participants with disease involvement of the bone marrow at baseline, repeat assessment will be done to confirm response.

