### 6.3.3 Partial Response (PR)

For PR determination in participants with measurable disease, all the following criteria must be met:

1. A  $\geq 50\%$  decrease in the sum of the product of the diameters (SPD) of up to 6 of the largest dominant nodes or nodal masses.
2. No increase should be observed in the size of other nodes, liver, or spleen, meeting the criteria for PD.
3. Splenic and hepatic nodules must regress by  $\geq 50\%$  in the SPD or, for single nodules, in the GTD.
4. With the exception of splenic and hepatic nodules, other organs should not have any measurable disease.
5. Bone marrow assessment is not required for PR determination.
6. No new sites of disease should be observed.
7. At least 1 PET-positive site of disease (required for the CT+PET assessment of PR).

For PR determination in participants with evaluable disease that is not measurable, all the following criteria must be met:

1. A  $\geq 50\%$  decrease in the SUVmax from baseline PET scan.
2. Bone marrow assessment is not required for PR determination.
3. No new sites of disease should be observed.
4. At least 1 PET-positive site of disease (required for the CT+PET assessment of PR).

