 Screening evaluations should be performed within 28 days of initiation of protocol therapy, with the following exceptions: Confirmation of diagnosis (no time limit); Serum or urine HCG, Electrocardiogram, and Lumbar puncture/Ommaya tap with glucose, protein, cell count/differential, cytology, and flow cytometry (within 14 days). See additional screening requirements in Section 2.2.

 Baseline evaluations should be performed within 14 days of initiation of protocol therapy, with the following exceptions: Urine and/or serum HCG (within 1 day); Bone marrow aspiration and biopsy (within 3 months), and Research samples (within 7 days). Ophthalmologic evaluation may be performed prior to or after initiation of study therapy (±28 days). Any Screening/Baseline tests performed within the specified time frame for start of treatment do not need to be repeated.

 Urine and/or serum HCG in participants of childbearing potential (within 14 days prior to initiation of Lenalidomide and again within 24 hours prior to initiation of Lenalidomide). See additional pregnancy testing requirements in Section 3.4.2.

 Patients on HBV prophylaxis will have HBV DNA levels obtained monthly during treatment. See additional information in Section 4.1.2.

 CT scans (C/A/P) are to be performed in restaging only if systemic disease present on baseline CT and/or PET imaging.

 PET will be performed at NIH after C6 to confirm CR or may be performed earlier in subjects with suspected CR based on interim imaging. PET body is to be performed in restaging only if systemic disease present on baseline CT and/or PET imaging.

 Performed to confirm disease status. Repeat after Cycles 1, 3 and 6 if CSF was positive for disease at baseline and the previous test result was positive. Once CSF cytology and flow cytometry are negative for disease, further CSF testing need not be repeated unless clinically indicated based on symptoms.

 To be performed within 3 months prior to starting protocol treatment. In follow-up: repeat after Cycle 6 if bone marrow was positive for disease at baseline.

 To be performed ±28 days from protocol treatment initiation. In follow-up: repeat after Cycles 3 and/or 6 if ophthalmologic evaluation was positive for disease at baseline.

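### The response-reference scan may be up to 28 days old and can predate other anti-lymphoma therapy allowed until 8 days before VIPOR, so ORR, CR rate and DOR may credit that therapy's effect to VIPOR

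*Combined protocol and SAP*

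**What the plan says.** **Washout.** Exclusion 2.1.2.2 reads: "Chemotherapy (excluding corticosteroids), radiation therapy, and/or monoclonal antibody ≤ 7 days prior to first administration of study treatment". The reason given is that "participants with relapsed CNS lymphomas often have existing neurologic conditions that mandate urgent therapy". Counting back from the first dose, therapy on day -8 or earlier is permitted.

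**Age of the scan.** Section 2.2.2.3 lists CT of chest, abdomen and pelvis, MRI brain and FDG-PET among the screening tests, and Section 2.2.2 sets the general limit: "Assessments and procedures to confirm study eligibility should be completed within 28 days prior to treatment initiation (unless otherwise noted"). The calendar in Appendix D (17.4.1) marks all three scans in the 28-day screening column and leaves their 14-day baseline column empty. Footnote 1 begins "Screening evaluations should be performed within 28 days of initiation of protocol therapy, with the following exceptions: Confirmation of diagnosis (no time limit") and goes on to give 14 days to the pregnancy test, the ECG and the CSF tap. Imaging is not among the exceptions. Footnote 2 adds: "Any Screening/Baseline tests performed within the specified time frame for start of treatment do not need to be repeated".

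**Scans from elsewhere.** Section 2.2.2 says "Assessments performed at outside facilities or on another NIH protocol within the timeframes below may also be used to determine eligibility" once consent is signed. PET is the exception, because it must be done at the NIH.

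**Use for response.** Section 6.3 says: "In addition to a baseline scan, restaging scans will be performed after cycles 1, 3, and 6". PR in PCNSL (6.3.1) is a halving of enhancing tumor. PR in SCNSL (6.3.3) is at least a 50% fall in the sum of products or, where disease is evaluable but not measurable, at least a 50% "decrease in the SUVmax from baseline PET scan". DOR (6.3.8) runs from the first recorded CR or PR.

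**The concern.** The two windows are set independently, and nothing orders the scan after the last prior treatment. If radiation, chemotherapy or an antibody is given after the reference scan but outside the last 7 days, restaging on VIPOR is compared with tumor as it stood before that other therapy. Any shrinkage it caused then counts toward a response to VIPOR, and a DOR clock may start from it. The study has a single arm, so no comparison group would reveal the error. It also cannot be undone later unless a post-therapy scan exists or the participant has been identified.

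**Working it through.** **1. The plan's own figure.** The only sized rule is in Section 10.2: 7 or more successes in 10, with 50% against 80%.
- P(X ≥ 7 | 10, 0.5) = (120 + 45 + 10 + 1)/1024 = 176/1024 = 0.1719, against the stated 17.2%.
- P(X ≥ 7 | 10, 0.8) = 0.8791, against the stated 87.9%.

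Both reproduce. Success (10.4.2) is completing at least two cycles without stopping for toxicity. No scan enters it, so this point leaves the rule untouched.

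**2. Overlap of the windows.**
- Earliest permitted reference scan: day -28 (2.2.2; Appendix D footnote 1).
- Latest permitted chemotherapy, radiation or antibody: day -8 (2.1.2.2).
- Longest lag from scan to later therapy: 28 - 8 = 20 days. Counted inclusively, therapy could fall on 21 calendar days.
- If the reference scan had to follow the last prior therapy, the overlap would be 0 days.

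**3. Does other text close the gap?**
- Section 2.4 sets 14 days for baseline evaluations but waives repeats of in-window screening tests, and the calendar has no baseline entry for imaging.
- Section 2.1.1.3 requires evaluable disease but does not say at what point relative to prior therapy.
- Section 3.8.2 lists failure to maintain eligibility before day 1 as an off-study criterion, but no re-scan is required that would detect it.
- Section 4.3.1 bars other lymphoma therapy during the study. It does not reach therapy given before enrollment but after an outside scan.
- Section 10.3.2 neither excludes nor identifies such a participant.

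**4. Weight of one participant.** Assume 10 response-evaluable participants. The response set in 10.3.2 is not fixed at 10; if it is smaller, each participant weighs more.
- One misattributed response: 1/10 = 10 points.
- Example: 5/10 = 50% (exact 95% CI 18.7 to 81.3) becomes 6/10 = 60% (26.2 to 87.8).
- One to three such participants, each a VIPOR non-responder turned into a responder by the other therapy: 10 to 30 points.

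**5. Expected bias, for illustration only.** Let p be the true ORR, b the share treated between scan and first dose, and q the chance that this therapy alone turns a non-responder into a PR. The expected observed ORR is p + (1 - p) × b × q. None of these inputs is in the documents. The ranges assumed are p 30 to 50%, b 10 to 40% and q 25 to 50%.
- Smallest bias: p = 0.50, b = 0.10, q = 0.25 gives 0.50 × 0.10 × 0.25 = 0.0125, about +1 point.
- Largest bias: p = 0.30, b = 0.40, q = 0.50 gives 0.70 × 0.40 × 0.50 = 0.14, or +14 points (30% to 44%).

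**The case against.** **The stated rationale.** A reader might infer from the urgent-therapy wording in 2.1.2.2 that the plan expects other treatment between scan and first dose. The text does not say so. It more naturally explains why VIPOR must start soon and a long washout is impractical. Urgency also makes a scan as old as 28 days less likely.

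**Exposure is narrow.** On a fair reading, Section 4.3.1 covers the time after enrollment. PET must be done at the NIH and follows consent, unless it was done under another NIH protocol. What remains is chiefly an MRI or CT done before consent. This stands as a limit on how often the problem arises, but it does not close the gap.

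**Only secondary endpoints.** Section 6.3 says response is not the primary endpoint, ORR and CR carry no decision threshold, and at 10 participants the exact interval already spans about 60 points. All of this is right, and it limits the importance of the point. But a wide interval expresses sampling error and does not correct a shift in one direction.

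**CR is an absolute state.** It requires no enhancement (6.3.1) or the full CR criteria of 6.3.2. A later reference scan would not change whether CR is met, unless it showed no disease left to evaluate. This stands: for CR rate, most of the benefit comes from identifying the participants concerned.

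**Growth before day 1.** A reader might also infer the opposite error, in which growth between an old scan and day 1 is read as poor response. That can happen with any 28-day screening scan, with or without other therapy. It does not come from the mismatch of windows, and ordering the scan after prior therapy would not address it in untreated participants. It is not part of this point.

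**Conclusion.** The concern holds within limits. A participant can follow the protocol exactly and still have a reference scan that predates other anti-lymphoma therapy by up to 20 days, and no section requires the scan to come after that therapy. ORR, CR rate and DOR can then include an effect that is not VIPOR's. The primary endpoint and the 7-of-10 rule are unaffected.

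The documents give no frequency. The 10 to 30 points should be read as a worst case for one to three participants out of an assumed 10, not as an expected bias. On the assumed inputs above, the expected bias is about +1 to +14 points. This is a modest weakness in the secondary endpoints that is cheap to repair before data accrue and hard to repair afterwards.

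**What to change.** Leave the washout as it is and change only the measurement rules.

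- **Section 2.2.2.3 and Appendix D footnotes 1 and 2:** state that the MRI, CT or PET serving as the response reference should be obtained after the last dose or fraction of prior anti-lymphoma therapy where feasible, by scheduling the already planned screening scan accordingly.
- **Flag:** where such therapy was given after that scan and no later pre-dose scan exists, flag the participant. Treatment history, including systemic therapy and radiation, is already taken at screening (2.2.2.1). The date of the last dose or fraction should be recorded with it, so that it can be set against the scan date.
- **Section 10.4.3:** report ORR, CR rate and DOR with and without flagged participants.

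The cost is slightly tighter scan scheduling and one added sensitivity listing; no repeat scan is made mandatory. Late effects of prior therapy that appear after the reference scan would still be credited to VIPOR, so misattribution is reduced but not removed.
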